5.2.4 Satisfaction of the providers obtained with post ventilation survey

#### 6. Study protocol

After providing informed consent, the subjects will receive premedication in the usual manner. Subjects will be placed on the operating room table in the supine position with the head in the neutral position on a pillow and elevated ~10 cm. The operators who will be performing mask ventilation are familiar with bag–valve mask ventilation, including the physicians, residents, and Anesthesia assistants. Medical students and anesthesia assistant students will not be involved in airway manipulation for the purposes of this study. All the operators will not be a

part of the study team. The operators will be provided with brief instructions before the induction (with a demonstration of the two techniques), with a photograph for each, as shown in **Fig. 4A** and 4B.

Figure 4A: Mask Ventilation using the V-E technique

Figure 4B: Ventilation via TTIP

Standard monitors for general anesthesia will be applied, including ECG, blood pressure measurement, pulse oximetry, and capnography. Pre-oxygenation via a medium-sized plastic mask will be carried out with a flow rate of 10-liter min of 100% O2 until the expired O2 concentration reaches  $\geq$ 80%. The mask will be connected to the breathing circuit and used for pre-oxygenation in both ventilation techniques.

Induction of anesthesia will be achieved by an intravenous bolus injection of fentanyl (1- $2\mu g/kg$ ), propofol (1–2 mg/kg). Thereafter, based on the clinical assessment of the care team, an appropriate level of sedation will be maintained with additional propofol.

When apnea is observed, the subjects will be ventilated with one of the two ventilation techniques in a randomized crossover manner. Ventilation will begin either with TTIP followed by mask ventilation (Group A) or with the reverse sequence, that is, mask ventilation followed by TTIP (Group B), as shown in Fig. 5. After induction, ventilation will be obtained with the ventilator set to pressure-control mode at a rate of 10 bpm, inspiratory-to-expiratory time ratio (I:E) of 1:2, peak inspiratory pressure (PIP) of 20 cm H2O, and no PEEP. Subjects will start with one technique (Step 1) and cross over to the other technique (Step 2), as shown in **Fig. 5**. The subjects in Group A will first be ventilated with the TTIP technique. If the subjects are adequately ventilated, as defined by carbon dioxide measured during exhalation in at least one of the first three consecutive breaths, ventilation will continue until completion of 10 breaths, for 1 min (Step 1). Subjects will then be ventilated with mask ventilation (Step 2). In Step 1, if

ventilation fails with the TTIP technique for all of the first three consecutive breaths, the subject will be crossed over to the mask ventilation (Step 2). If ventilation fails again with all the first three consecutive breaths after crossover, the study will be terminated. The routine care is resumed including tracheal intubation or LMA insertion. Once Step 2 is completed, routine care will be applied, including oral or nasal airway placement or placement of a laryngeal mask airway. If tracheal intubation was planned, either rocuronium or succinylcholine will be given to facilitate muscle relaxation followed by subsequent intubation. Subjects in Group B will follow the same protocol as that in Group A, with the exception that the sequence of applying the two ventilation techniques will be reversed, as shown in **Fig. 5**.

[figure not shown]

Figure 5: The algorithm of the study procedure. The numbers listed on the chart represent the number of breaths. At each Step, 10 breaths were targeted. NO= ventilation was not effective as assessed clinically; YES= ventilation was effective as assessed clinically.

Vital signs and parameters will continuously be recorded until the patient leaves the operating room. The monitor will not be masked, and the care team will be able to access it as they wish throughout the entire case. Once the patient arrives at PACU, the study team will assess the patient and record the vital signs 30 min after arrival and before discharge from the PACU. The study team will then call the patient 24 hours later to complete the QoR-15, which is a validated short form of the QoR-40 to assess any potential adverse effects. The data will include vital signs, incidence, and severity of nausea and vomiting, pain scale, sedation level, the satisfaction of the anesthesia, and medications administered in PACU. We will also record the

experience level of the attending, resident, or anesthesia assistant who is involved in the airway management with years of experience providing anesthesia.

#### 7. Data acquisition and analysis

All ventilatory settings and measured parameters displayed on the operating room ventilator (Datex Ohmeda AS/5, Helsinki, Finland), including expired tidal volume (VTeVTe), flow waveforms, end-tidal carbon dioxide partial pressure, exhaled carbon dioxide waveforms, and vital signs displayed on the monitor will be preserved electronically intra-operatively and video recorded from the time of pre-oxygenation and 5 minutes after intubation. The target number for ventilation is 10 breaths for both TTIP and mask ventilation techniques. Only the last five breaths (only three breaths for failed ventilation) will be used for final analysis to calculate the VTe and PIP. The mean of five breaths (three breaths if mask ventilation failed) is used as a single data point. Study team members converting the video recorded data to digital data will be blind to the interventions and the sequence of interventions. Once the study is completed and the digital data is collected, the study team members will be unblinded.

The primary analysis is to perform the McNemar test on the paired outcomes of all subjects. In addition to the McNemar test, we will find odds ratio estimate of failure for TTIP versus mask ventilation, together with its 95% confidence interval (CI), by stratifying on subject to handle dependence. Further, we will find the estimate of failure rate difference and its 95% Wald CI. We will consider and evaluation the covariance when estimating the standard error of failure rate difference.

We will perform multivariable analysis by using GEE method to estimate adjusted odds ratio of failure for TTIP versus mask ventilation. We will let the GEE model to include an odds ratio to accommodate within-subject association. The regression equation of the GEE model will include treatment (TTIP, mask ventilation), period (1, 2) and treatment-by-period interaction. The last two factors facilitates different carry-over effects for these two ventilation methods. If all factors will be significant, we will report the odds ratios of failure for TTIP versus mask ventilation at periods 1 and 2 separately. P values less than 0.05 will be considered as significant. All statistical analyses will be performed by using the SAS software (version 9.4, the SAS Institute, Cary, NC).

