#### 5. Outcomes

- 5.1 Primary outcome: The success rate of ventilation with TTIP vs. mask, defined as at least one of the first three breaths shows three phases of expired CO2 profile.
- 5.2 Secondary outcomes:
- 5.2.1 Expired tidal volume of ventilation with TTIP vs mask.
- 5.2.2 Peak inspiratory airway pressure achieved with TTIP vs. mask ventilation

5.2.3 Dynamic airway resistance is defined as the peak inspiratory flow divided by the corresponding airway pressure.

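### Tidal volume and peak pressure are averaged over late breaths after success but early breaths after failure, and no supportive analysis on a common window is planned (minor; secondary outcomes only)

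*Combined protocol and SAP*

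**What the plan says.** Section 5 lists expired tidal volume (VTe) and peak inspiratory pressure (PIP) as secondary outcomes; item 5.2.1 reads "Expired tidal volume of ventilation with TTIP vs mask". The primary outcome, item 5.1, is judged on the first three breaths.

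Section 6 ties the number of breaths to that result. After success, "ventilation will continue until completion of 10 breaths, for 1 min (Step 1"). Failure in the first step leads to a switch of technique: "ventilation fails with the TTIP technique for all of the first three consecutive breaths, the subject will be crossed over". Failure on the first three breaths of Step 2 ends the study procedure. The caption to Figure 5 confirms the target: "At each Step, 10 breaths were targeted".

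Section 7 then fixes the summary: "Only the last five breaths (only three breaths for failed ventilation) will be used for final analysis to calculate the VTe and PIP". The next sentence reads "The mean of five breaths (three breaths if mask ventilation failed) is used as a single data point", which mentions mask failure only.

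Every analysis named in Section 7 (McNemar test, odds ratio, failure rate difference, GEE) concerns failure. No method is named for VTe or PIP, and no analysis uses a window common to both techniques. Section 8 nevertheless predicts a significant improvement in expired tidal volume with TTIP.

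**The concern.** Together, the rules in Sections 6 and 7 mean that a success supplies breaths 6-10 and a failure supplies breaths 1-3. When one technique succeeds and the other fails in the same subject, the within-subject VTe difference compares a late window with an early one. If mask ventilation fails more often, as the plan assumes, these mismatched pairs are unbalanced: more of them place TTIP in the late window. The crossover does not cancel this, because the imbalance follows the difference in failure rates and not the order of the techniques.

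What is at stake is how a VTe difference is read. The planned summary alone does not show how far the result depends on when the breaths were taken.

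**Working it through.** **Inputs.** From Section 9: mask failure 34%, TTIP failure at most 20% (20% used), discordant pairs 25%, 200 evaluable subjects. The breath numbers 6-10 and 1-3 are inferred from Sections 6 and 7 and are the only reading that the rules allow. Section 6 words success a little differently from item 5.1, but both are read on the first three breaths, and they are treated as the same here.

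**The plan's own figures.** The documents give none for VTe or PIP. As a check on the inputs, two-sided McNemar power with a difference of 0.14, discordance 0.25 and n = 200 comes to 98.0-98.6% across the usual test variants (98.8-99.2% if 9/26 is not rounded), close to the stated 99.4%. Enrolment is 200 / (1 - 0.20) = 250, as stated.

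**Pairs by outcome.** The failure rate difference is 0.34 - 0.20 = 0.14.

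- Only mask fails: (0.25 + 0.14)/2 = 0.195, or 39 of 200
- Only TTIP fails: (0.25 - 0.14)/2 = 0.055, or 11 of 200
- Both fail: 0.34 - 0.195 = 0.145, or 29 of 200
- Both succeed: 1 - 0.25 - 0.145 = 0.605, or 121 of 200

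Mismatched windows: 39 + 11 = 50 pairs. Matching windows: 29 + 121 = 150 pairs.

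**Effect on the VTe difference.** Let dT and dM be the mean changes in VTe from breaths 1-3 to breaths 6-10 among TTIP and mask successes. The documents give neither. Assume that each is the same whether or not the other technique succeeded, and that VTe is compared as one mean paired difference (TTIP minus mask) over all pairs. Relative to a breaths 1-3 mean, the planned mean then shifts by:

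- mismatched pairs: 0.195·dT - 0.055·dM
- both-succeed pairs: 0.605·(dT - dM)
- both-fail pairs: 0
- total: 0.80·dT - 0.66·dM

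| dT (mL) | dM (mL) | Mismatched pairs | Both-succeed pairs | Total shift (mL) |
|---|---|---|---|---|
| -50 | -50 | -7 | 0 | -7 |
| 0 | 0 | 0 | 0 | 0 |
| +50 | +50 | +7 | 0 | +7 |
| +100 | +100 | +14 | 0 | +14 |
| +50 | 0 | +9.75 | +30.25 | +40 |
| 0 | +50 | -2.75 | -30.25 | -33 |

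With equal changes d the total is 0.14·d, all from mismatched pairs. With unequal changes most of it can come from pairs whose windows already match: 30.25/40 = 76% and 30.25/33 = 92% in the last two rows.

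**Sensitivity.** If TTIP halves failure, as Section 8 assumes (17%), then at 25% discordance the mismatched pairs number 42 and 8, and the equal-change shift is 0.17·d, or -8.5 to +17 mL for the same range of d. At 34% and 20%, the total does not depend on discordance; only the number of mismatched pairs does, from 28 (discordance 14%) to 108 (54%).

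**The case against.** The strongest reply is that this is a declared design choice. A failed technique has no later breaths, late breaths are a sensible description of settled ventilation, and using the three delivered breaths keeps failures in the comparison. All of that stands, and it is why the planned summary should remain.

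A second reply is that a breaths 1-3 analysis does not isolate the effect of timing. This also stands. A reader might infer that the difference between the two results would be the artefact of mismatched windows. That holds only if both techniques change equally from early to late breaths, and nothing in the documents supports this. If one technique settles differently from the other, the both-succeed pairs also move, and that movement is a real property of the techniques.

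Third, breaths 1-3 of Step 2 lie closest to the previous technique, no washout is described, and Section 7 itself allows for carry-over. That is a genuine drawback of the supportive analysis.

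Finally, no method is named for VTe at all, which limits what a supportive analysis can be set against. That is a separate gap. None of these replies removes the fact that the outcome selects the window and that no comparison free of that selection is planned.

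**Conclusion.** The point holds as a minor one, for secondary outcomes only. Under the Section 9 rates, a quarter of pairs (50 of 200) would compare VTe and PIP over different windows, 39 with TTIP late and 11 with mask late.

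A reader might go further and infer that the VTe comparison is biased towards TTIP. The documents do not support that: they give no early-to-late change in VTe, so size and direction are unknown and zero is possible. Part of the gap in discordant pairs is also a genuine effect of failure. The millilitre figures rest on assumed changes and an assumed method of comparison. With no VTe level, standard deviation or expected difference in the documents, they cannot be called large or small.

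PIP is probably less affected, since "ventilation will be obtained with the ventilator set to pressure-control mode at a rate of 10 bpm" with peak pressure set, and no PIP figure is claimed. The McNemar analysis and the sample size are untouched.

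**What to change.** In Section 7, before unblinding:

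- Keep the last-five-breath summary as planned.
- Prespecify a supportive analysis of VTe and PIP using the mean of breaths 1-3 for both techniques in every subject, by the same method as the main comparison of these outcomes (which Section 7 has yet to name).
- Report the number of pairs with mismatched windows, and show the difference between the two results separately for both-succeed pairs and mismatched pairs.
- State that this difference is not a pure timing artefact, because it can also reflect a real difference in how the techniques settle.
- Editorial only: reconcile the two consecutive sentences on the three-breath rule so that it covers failure of either technique.

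The cost is a few sentences and slightly more analysis work. No new data are needed: the ventilator display is "video recorded from the time of pre-oxygenation and 5 minutes after intubation", and the primary outcome already requires reading the first three breaths of each attempt. The drawbacks should be stated with the result: breaths 1-3 give a noisier mean, can include ineffective breaths from a technique that succeeded, reflect start-up, and in Step 2 are the most exposed to carry-over.

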#### 9. Sample Size Calculation

9.1 Our primary outcome is the rate of failed ventilation with mask vs. TTIP. Literature demonstrated that the rate of failed mask ventilation for obese patients with potential difficult mask ventilation is 9/26 (34%). We assume this failure rate (34%) for the mask ventilation in the proposed crossover study. We believe that for ventilation with TTIP, the failure rate is at most 20%. We also assume that in the proposed crossover study a quarter of subjects yield discordant outcomes. Two-sided McNemar test is used to evaluate effectiveness ot two ventilation methods. At the 5% significance level, the size of 200 subjects provides 99.4% power for proving superiority of TTIP to the mask ventilation. We assume a dropout rate of 20% and a total of 250 subjects will be enrolled. The enrolled subjects will be randomized at 1:1 ratio to two groups. For Group 1 we will deliver ventilation in mask-TTIP order. For Group 2 the TTIP-mask order will be employed.

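### The primary McNemar test and Wald interval ignore period and sequence: valid on average over 1:1 randomisation, but open to a shift given the realised split and slightly less powerful than a sequence-stratified analysis

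*Combined protocol and SAP*

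**What the plan says.** Section 6 describes a two-sequence, two-step crossover: "the subjects will be ventilated with one of the two ventilation techniques in a randomized crossover manner". Group A has TTIP first and Group B has mask first. Step 2 follows Step 1 within the same anaesthetic.

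Section 7 sets the primary analysis: "The primary analysis is to perform the McNemar test on the paired outcomes of all subjects". For the effect size it adds: "Further, we will find the estimate of failure rate difference and its 95% Wald CI". The covariance between the paired outcomes is to be taken into account, but neither the test nor the interval has a period or sequence term.

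Period appears only in the additional multivariable model: "The regression equation of the GEE model will include treatment (TTIP, mask ventilation), period (1, 2) and treatment-by-period interaction". On reporting from that model: "If all factors will be significant, we will report the odds ratios of failure for TTIP versus mask ventilation at periods 1 and 2 separately".

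Section 9 sizes the trial on the same period-free McNemar test: "At the 5% significance level, the size of 200 subjects provides 99.4% power for proving superiority of TTIP to the mask ventilation". On allocation it says: "The enrolled subjects will be randomized at 1:1 ratio to two groups". It names no blocking or other balancing method and allows for 20% dropout.

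**The concern.** Randomising the order lets a crossover separate the treatment effect from the period effect. Pooling the two orders in the primary analysis gives that up. If ventilation is systematically easier or harder in Step 2 than in Step 1, the pooled difference mixes some of that change into the treatment effect whenever the two sequences end up unequal. When they are equal, the period effect cancels from the estimate but stays in the variance, so the test is somewhat too cautious.

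The additional GEE does not repair the primary result. With a treatment-by-period interaction in the model, its treatment coefficient is not a single period-adjusted effect. Separate odds ratios by period are promised only if every factor is significant, and nothing is said about what is reported otherwise.

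At stake is how closely the reported difference and interval can be trusted for the split this trial obtains, plus a small amount of power.

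**Working it through.** **The plan's own figure.** Section 9 gives failure rates of 34% (mask) and 20% (TTIP), discordance of 25%, N = 200 and two-sided 5%. With d = 0.34 − 0.20 = 0.14 and pd = 0.25, power is Φ[(d√N − 1.96√pd) / √(pd − d²)] = 98.1%. Enumerating the chi-square test gives 98.6% and the Miettinen formula 99.0%. Using 9/26 in place of 34%, the three methods give 98.9%, 99.2% and 99.5%. The stated 99.4% is reproduced closely enough. Enrolment also follows: 200/(1 − 0.20) = 250.

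**Shift given the split.** Let d be mask failure minus TTIP failure, and π be failure risk in Step 1 minus Step 2, taken as additive and the same for both techniques. Mask comes second in Group A, so its expected paired difference is d − π. Mask comes first in Group B, so there it is d + π. Pooling gives

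E(pooled) = [nA(d − π) + nB(d + π)]/N = d + π(nB − nA)/N.

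The equal-weight mean of the two sequence differences is d whatever the split.

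**Variance.** Taking discordance as pd in both sequences, the within-sequence variances are pd − (d − π)² and pd − (d + π)². Their equal-split average is pd − d² − π². The Wald interval uses pd − d², and McNemar under the null uses pd. Each is too large by π².

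**Worked example under no treatment effect** (assumed π = 0.10; pd = 0.25; N = 200):
- McNemar standard error √(0.25/200) = 0.0354; rejection threshold 1.96 × 0.0354 = 0.0693.
- True standard deviation given the split √[(0.25 − 0.01)/200] = 0.0346.
- 100/100: 0.0693/0.0346 = 2.00, so type I error is about 4.5%.
- 110/90: shift 0.10 × 20/200 = 0.010. The tails are at (0.0693 − 0.010)/0.0346 = 1.71 and (0.0693 + 0.010)/0.0346 = 2.29, together about 5.4%.

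**Averaged over simple 1:1 randomisation.** (nB − nA)/N has mean 0 and variance 1/N. The shift therefore averages zero and adds π²/N to the variance: (pd − π²)/N + π²/N = pd/N, which is what McNemar uses under the null. Simulation agrees: about 5% type I error and zero mean bias, even at π = 17 points.

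**Range.** The documents give no period effect, so 0 to 17 points is an assumption (17 points is 36% failure in Step 1 and 19% in Step 2). The simulation uses a probit subject model, within-subject correlation 0.6, N = 200 and no treatment effect.

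| π (points) | McNemar type I error, 100/100 | McNemar type I error, 110/90 | Shift at 110/90 (points) |
|---|---|---|---|
| 0 | 4.9% | 4.9% | 0 |
| 5 | 4.9% | 5.1% | 0.5 |
| 10 | 4.4% | 5.4% | 1.0 |
| 17 | 3.8% | 6.1% | 1.7 |

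At 17 points and 110/90, Wald coverage is 93.6%. The sequence-stratified test rejects 5.1–5.3%. Under Binomial(200, 0.5), a split of 110/90 or worse in either direction has probability 18%, and 120/80 or worse 0.6%.

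**Power for 34% against 20%, averaged over simple randomisation.** With no period effect it is 98.1% for both methods. With the largest effect it is 96.7% (McNemar) and 98.0% (stratified).

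**The case against.** The strongest reply is that McNemar is a valid test here. Under the null, with order assigned at random, a discordant subject is equally likely to favour either technique whatever the period effect. Unlucky splits are already counted within the 5%. Dropout unrelated to sequence does not change this, and nothing in the documents suggests that dropout will differ by sequence. This stands.

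It also stands that the plan does not overlook period, since the GEE includes it, and that McNemar matches the sample-size method. Including period and its interaction to allow for carry-over is not the same as expecting a period effect, least of all one of 17 points.

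A reader might infer that type I error reaches about 13%. That figure (13.3%) needs both the 17-point effect and a 120/80 split. A reader might also infer a sizeable power loss at 110/90. With 110 subjects TTIP-first and the 17-point effect, McNemar has 92.7% against 98.0% for the stratified test. With the imbalance reversed, McNemar has 99.2%, because the estimate is then shifted upward.

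The reply does not remove the conditional point. The realised split will be known when the estimate is read, and the average over splits that did not occur does not correct the one that did.

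**Conclusion.** The point holds as an improvement in conditional bias and precision. The documents do not support the stronger reading that the primary p-value and interval lose their nominal properties: that is true only given an unequal realised split, or if dropout differs by sequence.

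The size is modest. For period effects of 5 to 10 points, type I error at 110/90 is 5.1–5.4% and the shift is 0.5 to 1.0 point, against a planned difference of 14 points. At the 17-point end it is 6.1% and 1.7 points. The average power gain is 0 to 1.3 points (98.0 − 96.7).

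These figures rest on an assumed period effect, the probit model with correlation 0.6, 200 evaluable subjects and, for the split probabilities and averages, simple randomisation. If the sequences are kept equal by a method the plan does not state, the shift vanishes and only the mild conservatism remains.

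**What to change.** In Section 7, make the primary analysis sequence-stratified. Within each randomised sequence, compute the mean paired difference (mask failure minus TTIP failure) and its variance. Take the equal-weight mean of the two as the primary estimate, with variance (VA + VB)/4, where VA and VB are the variances of the two sequence means. Base the test and 95% interval on it, and keep McNemar as supportive. It would also help to state in Section 9 how the sequences are kept balanced.

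The cost is a sentence or two in the plan and a few lines of SAS, with no extra data or subjects. With no period effect, average power is unchanged at 98.1%. The downside is that the large-sample version rejects about 5.1–5.3% under the null; a within-sequence score test or a re-randomisation test removes that excess.

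### Period-specific odds ratios from the GEE model are promised only when treatment, period and interaction are all significant, although only the interaction bears on whether they differ

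*Combined protocol and SAP*

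**What the plan says.** Section 7 makes the McNemar test on paired outcomes the primary analysis and adds a subject-stratified odds ratio and a failure-rate difference, each with a 95% CI. It then plans a further model: "We will perform multivariable analysis by using GEE method to estimate adjusted odds ratio of failure for TTIP versus mask ventilation". Its terms are listed: "The regression equation of the GEE model will include treatment (TTIP, mask ventilation), period (1, 2) and treatment-by-period interaction". Their purpose follows: "The last two factors facilitates different carry-over effects for these two ventilation methods". The reporting rule comes next: "If all factors will be significant, we will report the odds ratios of failure for TTIP versus mask ventilation at periods 1 and 2". The significance threshold is P below 0.05.

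No other sentence commits to results by period, states how the factors are coded, or says which odds ratio is given when the condition is not met. Section 6 (Study protocol) moves each subject from Step 1 to the other technique in Step 2 and describes no washout.

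**The concern.** A rule for showing the two period odds ratios separately should turn on whether they differ, and only the interaction term speaks to that. Requiring treatment and period to be significant as well adds two unrelated hurdles. Once an interaction is in the model, the meaning of those two terms also changes with the coding.

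Two things are at stake. Step 1 is the only comparison that cannot contain carry-over from the other technique, and the plan may never show it, even though this model is its own provision for carry-over. Also, two analysts following the text could report different output from the same data.

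**Working it through.** **The plan's own figures.** The documents give no figure for this rule. Section 9 (Sample Size Calculation) supplies the inputs: failure 34% with mask and 20% with TTIP, 200 subjects, 1:1 allocation (hence 100 per sequence), and "We also assume that in the proposed crossover study a quarter of subjects yield discordant outcomes". The two-sided McNemar power from these inputs is Φ[(0.14·√200 − 1.96·√0.25)/√(0.25 − 0.14²)] = Φ(2.08) = 98.1%, within 2 points of the stated 99.4%. The present point does not depend on it.

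**Algebra.** Let T1, T2, M1, M2 be the failure log odds for TTIP and mask in periods 1 and 2. The period log odds ratios are T1 − M1 and T2 − M2. The interaction is (T2 − M2) − (T1 − M1), which is their difference. The other terms depend on coding:
- Averaged (effect) coding: treatment is the mean of the two period log odds ratios, and period is the mean change over the two techniques.
- Reference coding: treatment is the log odds ratio in one chosen period, and period is the change within one chosen technique. There are four such codings.

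**Association within subject.** Joint failure = (0.20 + 0.34 − 0.25)/2 = 0.145. This gives φ = (0.145 − 0.068)/√(0.16 × 0.2244) = 0.406 and an odds ratio of (0.145 × 0.605)/(0.195 × 0.055) = 8.2.

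**Simulation.** There were 200,000 trials per scenario, with 100 subjects per sequence and φ held fixed. The mean model is saturated, so the estimates are the four cell logits. Wald tests at 5% use the within-subject covariance. Step 1 failure is 20% TTIP and 34% mask throughout. The Step 2 rates are assumptions, because the documents give no size or direction of carry-over.

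| Step 2 scenario (assumed) | Interaction significant | All three, averaged | All three, four reference codings | Rule not met although interaction significant (averaged; reference) |
|---|---|---|---|---|
| Effect reverses (mask 20%, TTIP 34%) | 76% | 0.3% | 48% | 99.6%; 36–37% |
| Mask falls to 20% | 25% | 3.7% | 0.8–24% | 85%; 5–97% |
| TTIP rises to 34% | 28% | 11% | 0.9–27% | 62%; 4–97% |
| TTIP falls to 10% | 27% | 18% | 0.1–26% | 33%; 3–99.7% |
| No carry-over | 5% | 0.4% | 1.1–1.4% | not computed |

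Holding the odds ratio or the 25% discordance fixed instead of φ moves the rates in the all-three columns by at most 2 points and the interaction column by at most 3.

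A separate run (20,000 trials, odds ratio held fixed) took TTIP failure as 10% then 34% and mask as 34% in both periods. The interaction was significant in 79% of trials. The rule was met in 77% under averaged coding and 2.5% under reference coding (mask, period 1). Neither type of coding is therefore safe.

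**The single odds ratio.** With mask failure after TTIP at 20%, period 1 gives (0.20/0.80)/(0.34/0.66) = 0.49 and period 2 gives 1.00. The average on the log scale is √0.485 = 0.70. Each of these is the treatment odds ratio under some coding.

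**Power of the interaction.** The logit variances are 1/(100 × 0.16) = 0.0625 and 1/(100 × 0.2244) = 0.0446. The covariance is 0.00077/(0.16 × 0.2244) = 0.0214. With no carry-over, SE = √[2(0.0625 + 0.0446 + 2 × 0.0214)] = 0.548. For 80% power the period odds ratios must differ by a factor of exp(2.80 × 0.548) = 4.6.

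**The case against.** The strongest reply is that this is an additional analysis. The McNemar test, the subject-stratified odds ratio and the rate difference are reported unconditionally, and the rule affects only the display of a supplementary model. That is right, and it limits the weight of the point.

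The text also says if, not only if, so it does not forbid period results. That stands too. The defect is that nothing else in the plan commits to them.

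The most striking row needs two opposite carry-overs at once, which nothing in the documents suggests. In the other three carry-over rows the interaction is significant in only 25–28% of trials, and under the most favourable coding the rule is met almost as often. There, low interaction power explains most of the non-reporting, and what the rows show is the effect of leaving the coding unstated. Where Step 2 moves both techniques the same way (mask 27% and TTIP 15%, or mask 41% and TTIP 27%), the interaction is significant in about 5% of trials and the rule hides almost nothing.

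The period odds ratios themselves are the same under every coding. Only the trigger and the meaning of the treatment term change. None of this makes the two extra conditions relevant, or settles which coding and which single odds ratio are meant.

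**Conclusion.** The concern holds, for the secondary GEE analysis only. That the treatment and period conditions are irrelevant follows from algebra and needs no assumption about carry-over. How often the rule withholds a detected difference does depend on assumed carry-over. Among simulated trials with a significant interaction, the rule was not met in 33% to 99.6% under averaged coding and in 3% to 99.7% across the reference codings. The spread is itself part of the finding: as written, the output cannot be reproduced from the text. The primary conclusion, sample size and power are untouched. The sentence should be corrected.

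**What to change.** Replace the conditional sentence in Section 7 with wording to this effect:

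> Failure rates, rate differences and odds ratios for TTIP versus mask, with 95% CIs, will be reported for period 1 and period 2 whatever the significance of any model term, together with the treatment-by-period estimate and its 95% CI. Period 1 is free of carry-over; period 2 may contain carry-over and is read as supportive.

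State the factor coding. Define the single adjusted odds ratio in advance. One option is the equally weighted average of the two period log odds ratios, with a note that it includes period 2. Making the interaction alone the condition would remove the logical error, but it is not recommended: its power is low, and in this two-sequence design it is aliased with sequence group. Leave the McNemar analysis as it is.

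The cost is a few sentences and one table, with no new data. The downside is precision, because Step 1 is a between-subject comparison:
- **Rate difference at the planned 14 points.** The Step 1 half-width is 1.96·√[(0.34 × 0.66 + 0.20 × 0.80)/100] = 12.2 points, so the CI is about 2 to 26. The paired half-width is 1.96·√[(0.25 − 0.14²)/200] = 6.7 points, so the CI is about 7 to 21.
- **Odds ratio of 0.49.** For period 1 the SE is √(0.0625 + 0.0446) = 0.327 and the CI 0.26 to 0.92. For the period average the SE is √[0.5(0.0625 + 0.0446 − 2 × 0.0214)] = 0.179 and the CI 0.34 to 0.69.

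Readers may over-read a chance difference between two noisy period estimates, which is why the interaction CI should stand beside them.
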